9.1.1. Relationship to Study Drug

Adverse events will be classified as “related” to study treatment if the relationship was rated by the investigator as possibly related or probably related. Adverse events related to any study drug component (relugolix or placebo and E2/NETA or placebo) will be considered as related to study drug.

9.1.2. Severity of Adverse Event

Grade 2 or higher adverse events will be summarized by SOC, PT, and/or maximum severity, relationship to study treatment.

9.1.3. Serious Adverse Event

Serious adverse events throughout the parent and extension studies will be summarized by SOC, PT, and/or maximum severity, relationship to study treatment.

The data handling conventions for and the definition of a serious adverse event are discussed in this section. All deaths during the studies, including the post treatment follow-up period, and deaths that resulted from a process that began during the studies, should be included in the analysis. For more details, deaths occurring during the following time periods or under the following conditions should be considered:

- Deaths occurring during participation in either the parent study or study MVT-601-3003;
- Deaths occurring after a patient leaves a study, or otherwise discontinues study drug, whether or not the patient completes the study to the nominal endpoint, if the death:
 - Is the result of a process initiated during the study or other drug exposure, regardless of when it actually occurs; or
 - Occurs within a time period that might reflect drug toxicity for a patient leaving a study or otherwise discontinuing drug.

9.1.4. Adverse Event Leading to Withdrawal of Study Drug

Adverse events leading to withdrawal of study drug are those adverse events collected from the adverse event electronic case report form (eCRF) pages with “drug withdrawn” as the action taken with study drug.

Adverse events with “drug withdrawn” as action taken due to any one of the components of study drug will be considered as leading to withdrawal of study drug.

9.1.5. Adverse Events Leading to Dose Interruption

Adverse events leading to dose interruption are those adverse events collected from the adverse event eCRF pages with “drug interrupted” as their action taken with study drug.

Adverse events with “drug interrupted” as action taken due to any one of the components of study drug will be considered as leading to dose interruption.

9.1.6. Adverse Events Resulting to Fatal Outcome

Adverse events resulting in a fatal outcome are those adverse events collected from the adverse event pages with “fatal” as their outcome.

The fatal events, if any, will be provided in a by-subject listing.

9.1.7. Adverse Event Categories

In addition, adverse event categories defined in [Table 12](#) will be summarized by decreasing frequency of PT under each safety population.

Table 12: Constitution of Adverse Event Categories

Category	Search Criteria
Bone health events	Osteoporosis/Osteopenia SMQ (broad) Fracture (custom SMQ): All preferred terms including the term “fracture,” excluding “Tooth fracture” and “Fracture of penis”
Hepatic transaminase elevations	Drug-related hepatic disorders – comprehensive SMQ (narrow)
Carbohydrate and lipid metabolic effects	Dyslipidemia SMQ (broad) Hyperglycemia/new onset diabetes mellitus SMQ (narrow)
Vasomotor symptoms	The following five Preferred Terms will be included: Hyperhidrosis; Feeling hot; Hot flush; Night sweats; Flushing.
Mood disorders	MedDRA Depression and Suicide/Self-Injury SMQ (broad)

Abbreviations: MedDRA = Medical Dictionary for Regulatory Activities; SMQ = Standardised MedDRA Query.

9.1.8. Exposure-adjusted Adverse Events

Adverse events by time to onset and an exposure-adjusted adverse event analysis will be provided. The exposure-adjusted adverse event rate will be summarized by system organ class and preferred term for each parent study treatment group, where the exposure-adjusted adverse event rate is calculated as number of patients with a particular adverse event by total exposure-time among patients at risk of an initial occurrence of the event. Exposure-time is derived as exposure to any study drug throughout the parent and extension study.

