1.1. Schedule of Activities

Table 1: Schedule of Activities for Study MVT-601-3003

PERIOD	OPEN-LABEL TREATMENT									SAFETY FOLLOW-UP
	VISIT NAME (Timing is relative to MVT-601-3001/-3002)	Week 24/Baseline (Week 24 of Parent Study; Baseline of Extension Study)	Week 28	Week 32	Week 36	Week 40	Week 44	Week 48	Week 52 ^a (or Early Termination of Study Drug)	
Visit Window (days)	Parent Study Day 169 - 10 to + 20	± 7	± 7	± 7	± 7	± 7	± 7	± 10	-	- 3 to + 18
Informed Consent	X ^d									
Review Eligibility Criteria	X									
Concomitant Medications ^e	X ^f	X	X	X	X	X	X	X	X	X
Vital Signs (BP, HR, Temperature)	X ^g	X	X	X	X	X	X	X	X ^h	X
Weight	X ^g			X				X	X ^h	
Complete Physical Examination	X ^g							X		
Visual Acuity ⁱ	X ^g									
Signs and Symptoms-Directed Physical Examination ⁱ		X	X	X	X	X	X		X ^h	X
12-Lead ECG ^k	X ^g							X	X ^h	
Clinical Laboratory Tests ^l	X ^{g,m}	X	X	X	X	X	X	X ^m	X ^h	X
Pharmacodynamics Sample ⁿ	X ^{g,m}							X ^m	X ^{h,m}	
Urinalysis	X ^g							X	X ^h	
Pregnancy Test (Urine)	X ^g	X	X	X	X	X	X	X	X ^h	X

PERIOD	OPEN-LABEL TREATMENT									SAFETY FOLLOW-UP
VISIT NAME (Timing is relative to MVT-601-3001/-3002)	Week 24/Baseline (Week 24 of Parent Study; Baseline of Extension Study)	Week 28	Week 32	Week 36	Week 40	Week 44	Week 48	Week 52 ^a (or Early Termination of Study Drug)	Un-scheduled ^b	Follow-Up ^c (~30 days after last dose of study drug)
Visit Window (days)	Parent Study Day 169 - 10 to + 20	± 7	± 7	± 7	± 7	± 7	± 7	± 10	-	- 3 to + 18
Transvaginal Ultrasound ^o	X ^g							X ^p	X ^h	
Bone Densitometry ^d	X ^g			X				X ^{p,r}	X ^h	
Endometrial Biopsy	X ^{g,s}							X ^p	X ^h	
Dispense Study Treatment	X	X	X	X	X	X	X		X ^h	
Patient Paper Diary ^t	X	X	X	X	X	X	X	X	X	
Dispense Feminine Products	X	X	X	X	X	X	X		X ^h	
Feminine Product Collection and Venous Blood Sample ^u	X ^g	X	X	X	X	X	X	X	X ^h	
Treatment Compliance		X	X	X	X	X	X	X	X ^h	
Take Study Drug Dose in Clinic ^v	X ^w							X	X ^h	
Daily Self-Administration of Study Treatment ^v		X								
MIQ ^x	X ^g	X	X	X	X	X	X	X	X ^h	X
UFS-QoL Questionnaire ^x	X ^g			X				X	X ^h	
EQ-5D-5L Questionnaire ^x	X ^g							X	X ^h	
Adverse Event Collection ^y	X ^z	X	X	X	X	X	X	X	X	X
Status of Menstruation Recovery										X ^{aa}

BP, blood pressure; ECG, electrocardiogram; EQ-5D-5L, European Quality of Life Five-Dimension Five-Level Scale; HR, heart rate; MIQ, Menorrhagia Impact Questionnaire; UFS-QoL, Uterine Fibroid Symptom and Health-Related Quality of Life

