- ^a The week 52 visit must occur on or after the 1-year anniversary of Study Day 1 in the parent study. The timing of the visit should also be at least 28 weeks (± 10 days) from the actual date of the Week 24/Baseline visit.
- ^b Unscheduled visits may be conducted at the investigator's discretion when needed. The reason for the visit will be captured in the source documents.
- ^c The Follow-up visit may be waived if the patient enrolls directly into another relugolix clinical study upon completion of the Week 52 visit.
- ^d May be signed up to 30 days prior to the Week 24/Baseline visit or during the Week 24/Baseline visit. Enrollment in MVT-601-3003 is defined by administration of the first dose of MVT-601-3003 study drug.
- ^e Record all prescription and nonprescription drug and supplements taken from the Week 24/Baseline visit through the Safety Follow-Up period. Concomitant medications with start date prior to the first dose of study drug for MVT-601-3003 should be reported as concomitant medications in the parent study (MVT-601-3001 or MVT-601-3002). Concomitant medications initiated during the MVT-601-3001 or MVT-601-3002 studies and ongoing at the time of the first dose in Study MVT-601-3003 will be recorded in the electronic case report form.
- ^f Concomitant medications are recorded both for the parent study and for MVT-601-3003 at the Week 24/Baseline visit. (See footnote c for further details).
- ^g This is a parent study (MVT-601-3001 or MVT-601-3002) Week 24 procedure that serves as the Week 24/Baseline procedure for MVT-601-3003 and is covered under the informed consent for the parent study.
- ^h The indicated procedure may be performed at the Unscheduled visit based on the purpose of the visit (eg, follow-up for an adverse event or abnormal laboratory test).
- ⁱ See parent study protocols (MVT-601-3001 or MVT-601-3002) for instructions on testing visual acuity.
- ^j The exam may include a gynecologic examination, if indicated based on signs and symptoms.
- ^k The 12-lead ECGs will be submitted for central reading.
- ^l Clinical laboratory tests at each visit include clinical chemistries and a complete blood count. At the Week 24/Baseline visit and Week 52 visit, additional tests include: fasting (at least 8 hours) glucose, lipid profile, and hemoglobin A1c.
- ^m Samples should be obtained in a fasted state (at least 8 hours). Water is allowed during the fasting period.

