6. STUDY DRUG EXPOSURE AND COMPLIANCE

All analyses of extent of exposure to study drug and compliance will be summarized by actual treatment received in the parent study. Extent of exposure to relugolix and E2/NETA during the extension study will be summarized for patients in the Extension Safety population. Overall exposure to relugolix (with or without E2/NETA), overall exposure to E2/NETA, and overall exposure to any study drug (relugolix [with or without E2/NETA] and placebo) throughout the parent study and extension study will be summarized by parent study treatment group. Compliance with open-label study drug during the extension study for the Extension Safety population will be summarized by parent study treatment group. Overall compliance with study drug throughout the parent study and extension study will be summarized by parent study treatment group. Exposure to and compliance with relugolix and E2/NETA will be summarized separately and will be based on the drug accountability case report forms.

Study drug exposure summaries will include the total dosage of relugolix and E2/NETA taken in milligrams and treatment duration. Total dosage of relugolix and E2/NETA taken during the extension study and overall, throughout the parent and extension studies, will be summarized by parent study treatment group. Treatment duration during the extension study and overall with any study drug (relugolix, E2/NETA, or placebo) will be summarized by parent study treatment group.

Study drug compliance will be summarized for the extension study treatment period and for the overall parent and extension study treatment period, and will be calculated as follows:

$$(\text{total tablets taken} / \text{total tablets expected to be taken}) \times 100$$

The total tablets taken will be calculated as:

$$(\text{total tablets dispensed} - \text{total tablets returned})$$

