9.1. Adverse Events

Adverse events will be collected from the time of the first dose of open-label study drug through the safety follow up visit approximately 30 days after the last dose of open-label study drug (the end of extension treatment period), or the date of initiation of another investigational agent or hormonal therapy or surgical intervention or entering the MVT-601-035 study, whichever occurs first. Serious adverse events reported to the investigator after the safety reporting period should be reported to the sponsor if the investigator assesses the event as related to study drug.

The severity of all treatment-emergent adverse events will be evaluated by the investigator based on the National Cancer Institute's Common Terminology Criteria for Adverse Events (CTCAE) and will be coded to preferred term and system organ class using MedDRA 22.0 or higher.

A treatment-emergent adverse event is defined as any adverse event that occurs after administration of the first dose of parent study drug.

Adverse event summaries will be based on treatment-emergent adverse events in the parent and extension studies, unless otherwise specified. All adverse events in the parent and extension studies will be listed in by-patient listings.

The following tabular summaries that include the number and percentage of patients will be provided:

- Overview of adverse events;
- All adverse events;
 - By SOC and PT;
 - By decreasing frequency of PT;
 - By SOC, PT, and maximum severity;
 - Study drug-related per investigator by SOC and PT;
 - By time to onset, SOC and PT;
- Grade 3 or above adverse events;
 - By SOC and PT;
 - By decreasing frequency of PT;
 - Study drug-related per investigator by SOC and PT;
- Grade 2 or above adverse events;
 - By SOC and PT;
 - By decreasing frequency of PT;
 - By SOC, PT, and maximum severity;

- Study drug-related per investigator by SOC and PT;
- Adverse events leading to study drug withdrawal;
 - By SOC and PT;
 - By decreasing frequency of PT;
- Adverse events leading to dose interruption;
 - By SOC and PT;
 - By decreasing frequency of PT;
- Adverse events resulting in fatal outcome;
 - By decreasing frequency of PT;
- Serious adverse events;
 - By SOC and PT;
 - By decreasing frequency of PT;
 - By SOC, PT, and maximum severity;
 - By SOC, PT, and relationship to study drug;
- Adverse events of clinical interest (ALT or AST $\geq 3 \times$ ULN);
 - By SOC, PT, and maximum severity;
 - By decreasing frequency of PT.

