- Adverse events with first onset during the extension study;
 - By SOC and PT;
 - By decreasing frequency of PT;

Additionally, adverse event categories defined in [Table 12](#) will be summarized by decreasing frequency of PT.

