9.2. Laboratory Data

Laboratory parameters, including chemistry and hematology panels, specified as per protocol for the parent and extension studies, and collected from the central laboratory will be tabulated and presented in by-patient listings. Urinalysis and hepatitis virus serological test results will be provided in by-patient listing only.

The National Cancer Institute CTCAE Grading Scale with numeric component will be used to categorize toxicity grade for laboratory parameters (CTCAE v5.0, dated 27 Nov 2017). Parameters that have criteria available for both low and high values (eg, hypercalcemia for a high value of calcium and hypocalcemia for a low value of calcium) will be summarized for both criteria (low and high). Patients will only be counted once for each criterion. The same patient can be counted for both criteria if she has laboratory values meeting each criterion. Shift tables will be provided for each gradable parameter to summarize Baseline toxicity grade versus worst post-Baseline toxicity grade throughout the parent and extension studies. For laboratory parameters that are not gradable by the CTCAE, a shift table based upon the normal range (low,

normal, and high) will be provided for each parameter to summarize the Baseline versus worst post-Baseline results throughout the parent and extension studies.

Boxplots of laboratory values over time, including visits in both the parent study and extension study, will be plotted for key laboratory parameters. These laboratory parameters include, but are not limited to, hematology (hemoglobin, platelets, leukocytes, neutrophils), creatinine, glomerular filtration rate, and hepatic function panel (alanine aminotransferase [ALT], aspartate aminotransferase [AST], alkaline phosphatase [ALP], and total bilirubin).

The change from Baseline to each post-Baseline study visit will be presented by parent study treatment group for each laboratory test in both tables and figures.

The number and proportion of patients with liver test elevations will be presented by parent study treatment group. Liver test elevations are assessed by using post-Baseline results for ALT, AST, ALP, and total bilirubin based on the definitions presented in [Table 13](#).

Table 13: Categories of Liver Test Elevations

Laboratory Test	Category
ALT or AST	ALT or AST > ULN < 3 × ULN ALT or AST ≥ 3 × to < 5 × ULN ALT or AST ≥ 5 × to < 10 × ULN ALT or AST ≥ 10 to < 20 × ULN ALT or AST ≥ 20 × ULN

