APPENDIX 1: LIST OF PRE-DEFINED THRESHOLD IN SELECTED CHEMISTRY AND HEMATOLOGY TEST RESULTS

Chemistry Laboratory	
Liver Function	
ALT > ULN and < 3× ULN	Total BILI > ULN
ALT ≥ 3× ULN and < 5× ULN	Total BILI > 2× ULN
ALT ≥ 5× ULN and < 10× ULN	
ALT ≥ 10× ULN and < 20× ULN	ALT or AST ≥ 3× ULN and Total BILI > 2× ULN
ALT ≥ 20× ULN	ALT or AST ≥ 3× ULN and Total BILI > 2× ULN and ALP < 2× ULN
AST > ULN and < 3× ULN	GGT > ULN and < 3× ULN
AST ≥ 3× ULN and < 5× ULN	GGT ≥ 3× ULN and < 5× ULN
AST ≥ 5× ULN and < 10× ULN	GGT ≥ 5× ULN and < 10× ULN
AST ≥ 10× ULN and < 20× ULN	GGT ≥ 10× ULN and < 20× ULN
AST ≥ 20× ULN	GGT ≥ 20× ULN
ALT or AST > ULN and < 3× ULN	
ALT or AST ≥ 3× ULN and < 5× ULN	
ALT or AST ≥ 5× ULN and < 10× ULN	
ALT or AST ≥ 10× ULN and < 20× ULN	
ALT or AST ≥ 20× ULN	
Renal Function	
CR > 1.5 mg/dL and > BL	GFR < 15 mL/min per 1.73 m ²
CR > 50% increase from BL	GFR ≥ 15 - < 30 mL/min/1.73 m ²
	GFR ≥ 30 - < 60 mL/min min/1.73 m ²
	GFR ≥ 60 - < 90 mL/min min/1.73 m ²
	GFR ≥ 90 mL/min min/1.73 m ²

Chemistry Laboratory	
Metabolic Parameters	
Fasting Glucose	Highest Postbaseline Glucose
< 100 mg/dL at BL	Gluc \geq 200 mg/dL and > BL
< 100 mg/dL at Week 24	Gluc \geq 200 mg/dL and \geq 126 BL
\geq 100 - < 126 mg/dL at Week 24	Gluc \geq 500 mg/dL
\geq 126 mg/dL at Week 24	Gluc \geq 500 mg/dL and \geq 126 BL
\geq 100 - < 126 mg/dL at BL	Total CHOL > 200 mg/dL and > BL
< 100 mg/dL at Week 24	Total CHOL increase > 30 mg/dL from BL
\geq 100 - < 126 mg/dL at Week 24	
\geq 126 mg/dL at Week 24	HDL < LLN and < BL
	LDL > ULN and > BL
\geq 126 mg/dL at BL	TRIG > ULN and > BL
< 100 mg/dL at Week 24	
\geq 100 - < 126 mg/dL at Week 24	
\geq 126 mg/dL at Week 24	
Electrolytes and other Chemistry Parameters	
ALB < LLN and < BL	CK > 2 \times ULN and > BL
ALB > ULN and > BL	CK > 5 \times ULN and > BL
	CK > 10 \times ULN and > BL
ALP > 2 \times ULN and > BL	
ALP > 5 \times ULN and > BL	MG < LLN and < BL
ALP > 10 \times ULN and > BL	MG > ULN and > BL
CA < LLN and < BL	PHOS < LLN and < BL
CA > ULN and > BL	PHOS > ULN and > BL

K < LLN and < BL	NA < LLN and < BL
K > ULN and > BL	NA > ULN and > BL
Hematology Laboratory	
HCT < LLN and < BL	NEUT < LLN and < BL
HCT decrease ≥ 10 from BL	NEUT > ULN and > BL
HGB ≤ 10.5 g/dL and < BL	BASO < LLN and < BL
HGB decrease > 1 g/dL from BL	BASO > ULN and > BL
MCV < LLN and < BL	EOS < LLN and < BL
MCV > ULN and > BL	EOS > ULN and > BL
	EOS > 5% and > BL
WBC < LLN and < BL	
WBC > ULN and > BL	PLT < LLN and < BL

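### Group C's exposure-adjusted AE rate and worst-value lab shifts merge 24 placebo weeks with 28 relugolix weeks, and the fasting-glucose category shift has no Week 52 rows

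*SAP*

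**What the plan says.** **Rate.** SAP 9.1.8 reports an exposure-adjusted rate by system organ class and preferred term for each parent study group: patients with the event, divided by exposure time among those at risk of a first occurrence. On the denominator it says: "Exposure-time is derived as exposure to any study drug throughout the parent and extension study". SAP 6 makes clear that placebo counts, listing "overall exposure to any study drug (relugolix [with or without E2/NETA] and placebo" among the exposure summaries. On the numerator, SAP 9.1 says: "A treatment-emergent adverse event is defined as any adverse event that occurs after administration of the first dose of parent study drug". The one adverse event table in SAP 9.1 restricted to the extension is "Adverse events with first onset during the extension study", given as numbers and percentages of patients.

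**Laboratory shifts.** SAP 9.2 says the tables for gradable parameters will "summarize Baseline toxicity grade versus worst post-Baseline toxicity grade throughout the parent and extension studies", and treats non-gradable parameters the same way. The safety paragraph of the protocol synopsis describes shifts from parent Baseline to each later visit instead.

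**Fasting glucose.** Appendix 1 crosses three Baseline strata with three outcome categories. Every outcome row carries the same time point, for example "< 100 mg/dL at Week 24". Protocol 1.1, footnote l, schedules the test later as well: "At the Week 24/Baseline visit and Week 52 visit, additional tests include: fasting (at least 8 hours) glucose, lipid profile, and hemoglobin A1c".

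**Visit windows.** Protocol 1.1 allows the Week 24/Baseline visit at "Parent Study Day 169 - 10 to + 20" days. SAP 4.3.8, Table 2, closes Week 24 at Day 183 and runs Week 28 from Day 184 to Day 211.

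**The concern.** Group C is the group that starts relugolix in this study, so its extension data are new-exposure safety data. A rate that adds its placebo weeks to its relugolix weeks equals the on-relugolix rate only if the event is equally frequent in the two periods. If the event is commoner on relugolix the pooled figure is too low; if it is commoner on placebo the figure is too high. Because only the initial occurrence counts, a woman whose event began on placebo cannot contribute a relugolix-period event.

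The worst-value shifts have the same weakness: a Group C abnormality seen only on placebo looks the same as one seen on relugolix. For fasting glucose, the category table ends before Group C has taken any relugolix, and for every group it omits the 52-week result. The window mismatch can show a value taken before the first extension dose under an on-treatment visit label.

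**Working it through.** **1. The plan's own time figures.** Inputs: 24 weeks of placebo for Group C (SAP 1), 28 weeks of open-label treatment (SAP 2.1), 52 weeks in total (SAP 1.1). 24 + 28 = 52. The target days in Table 2 agree: (169 − 1)/7 = 24 weeks and (365 − 169)/7 = 28 weeks. For a Group C completer, 24/52 = 46.2% of exposure time is placebo and 28/52 = 53.8% is relugolix with E2/NETA.

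**2. Rare event.** Let k be the ratio of the placebo rate to the relugolix rate, and e the extension weeks. The documents give no adverse event rates, so k is an assumption.

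Pooled rate ÷ relugolix-period rate = (24k + e)/(24 + e)

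| k | e = 28 (completers) | e = 12 (illustration) |
|---|---|---|
| 0 | 28/52 = 0.54 | 12/36 = 0.33 |
| 0.5 | 40/52 = 0.77 | 24/36 = 0.67 |
| 1 | 52/52 = 1.00 | 36/36 = 1.00 |
| 2 | 76/52 = 1.46 | 60/36 = 1.67 |

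**3. Commoner events, risk time stopped at the first event.** Assume a constant hazard in each period, λ0 on placebo and λ1 on relugolix, with a = 168/365.25 = 0.460 years and b = 196/365.25 = 0.537 years. Put S0 = exp(−λ0·a), T0 = (1 − S0)/λ0 (or a if λ0 = 0) and T1 = S0·(1 − exp(−λ1·b))/λ1.

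Pooled rate = [(1 − S0) + S0·(1 − exp(−λ1·b))] / (T0 + T1)

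Example, 0 then 40 per 100 patient-years: 1 − exp(−0.4 × 0.537) = 0.193; T1 = 0.193/0.4 = 0.483; pooled rate = 0.193/(0.460 + 0.483) = 0.205, or 20.5 per 100 patient-years.

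| Placebo / relugolix, per 100 PY | Pooled | Pooled ÷ relugolix |
|---|---|---|
| 0 / 10 | 5.3 | 0.53 |
| 5 / 10 | 7.6 | 0.76 |
| 10 / 10 | 10.0 | 1.00 |
| 20 / 10 | 14.8 | 1.48 |
| 0 / 40 | 20.5 | 0.51 |
| 20 / 40 | 30.0 | 0.75 |

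SAP 9.1.8 does not say whether time stops at the first event. With full exposure time in the denominator, 0/10 gives 5.2 and 20/10 gives 13.6, so that ambiguity matters less than the pooling.

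**4. Laboratory shifts.** SAP 9.2 takes one worst value per patient over both studies. In Group C that value may come from either period, and the table does not show which.

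**5. Fasting glucose.** Appendix 1 has 3 × 3 = 9 outcome rows, all at Week 24 and none at Week 52. The highest post-Baseline glucose rows use 200 and 500 mg/dL, so they do not replace the 100 and 126 mg/dL fasting categories.

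**6. Windows.** Permitted Week 24 visit: Day 169 − 10 to Day 169 + 20, or Days 159 to 189. Table 2 assigns Days 184 to 189 to Week 28 (target Day 197). Such a sample is 197 − 189 = 8 to 197 − 184 = 13 days from target, while an on-schedule Week 28 visit (197 ± 7, Days 190 to 204) is at most 7 days away. The closest value is used, so where both exist the Week 24 value drops out of the by-visit table. HbA1c and fasting lipids are scheduled in the extension only at Weeks 24 and 52, so for them the pre-dose value would appear as Week 28. The longer windows in Tables 3 to 6 end Week 24 at Day 196 and are not affected.

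**The case against.** The strongest reply is that the periods are already partly separated. SAP 9.1 plans the extension-onset table and a table by time to onset; SAP 9.2 plans by-visit laboratory changes and Appendix 1 thresholds on the last on-treatment value, which in Group C is normally a relugolix value. Extension treatment is nominally 28 weeks and its duration is summarized by parent group, so a reader could approximate a relugolix-period rate. Pooling over both studies also follows Protocol 9 and 9.5, and the study is descriptive with no formal comparisons. This stands as mitigation and keeps the point from being critical. But none of these outputs is a period-specific rate, a period-specific worst-value shift or a Week 52 fasting-category shift, and a descriptive rate should still belong to an identifiable treatment.

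A second reply is that a pre-extension reference value departs from the protocol's rule that parent Baseline is the reference for change. That is true and should be stated openly. SAP 1.1 permits other references where specified, and the parent-Baseline tables would be kept.

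Third, Group B also mixes regimens, relugolix alone for 12 weeks and then with E2/NETA. That is correct, but all of its time is on relugolix; the placebo problem is confined to Group C.

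Fourth, the sizes are hypothetical, and the 12-week column would describe the whole group only if every patient left then. Both are granted: the figures show sensitivity and are not predictions.

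Fifth, the window mismatch is a separate matter that touches all groups. That is also right. It is included because in Group C it puts a placebo value under a relugolix visit; how often visits fall on Days 184 to 189 is not known.

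**Conclusion.** The point holds. As written, Group C receives one rate per term across two different treatments, and its worst-value laboratory shifts cannot be attributed to either. For completers and rare events the pooled rate is 54% to 146% of the relugolix-period rate as the assumed placebo-to-relugolix ratio runs from 0 to 2, with no distortion at a ratio of 1. The direction depends on the event. The rate and shift points concern Group C only.

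The glucose gap is narrow: only the Week 52 fasting-category shift is missing, while by-visit values, worst-value shifts, highest post-Baseline glucose and HbA1c thresholds remain. The window problem is limited to Table 2 and Days 184 to 189. The plan should be changed because the remedy is cheap, though other planned outputs soften the consequence.

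**What to change.** - In SAP 9.1.8 and 9.2, report Group C exposure-adjusted rates and worst-value shifts separately for the placebo and relugolix periods, split at Extension Study Day 1 (already defined in SAP 4.3.4). For the relugolix-period shift, use the last value before the first extension dose as the reference, and say that this is an exception to parent Baseline. Keep the pooled outputs.
- In Appendix 1, add Week 52 rows to the fasting-glucose category shift and keep the Week 24 rows.
- In SAP 4.3.8, Table 2, assign any value collected before the first extension dose to Week 24 or earlier.

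The cost is SAP wording, a few more Group C columns and some programming on data already held. The drawback is more columns to read and fewer events per period in Group C.
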